6.4. Interim Analysis

An interim analysis for safety and futility is planned for when approximately 86 subjects (approximately 50% of subjects) have completed the Day 95/Early Termination Visit. Enrollment will continue during this analysis. Details of the interim analysis will be provided in a separate document.

An independent unblinded data monitoring committee will review the interim data and provide recommendations for study continuation.

7. STATISTICAL ANALYSES

7.1. Subject Disposition

The number of subjects included in each study population will be summarized by treatment group and overall. Subjects excluded from the safety, ITT, mITT, or PP populations will be listed.

The frequency counts and percentages of subjects screened, enrolled, completed and/or withdrawn from the study, as well as the reason for withdrawal from study will be summarized by treatment group and overall.

A listing of disposition data will be provided. Screen failure reasons will also be listed. In addition, a listing for inclusion/exclusion criteria will be presented.

25-April-2022

7.2. Protocol Deviations

Protocol deviations will be summarized by deviation classification (major/minor), and by treatment group and overall. A listing of all protocol deviations will be presented.

7.3. Demographics and Baseline Characteristics

Demographics and baseline characteristics will be summarized by treatment group and overall, for the safety, mITT, and PP populations.

Age, height (at baseline), body weight (at baseline), BMI in kg/m^2 , and time since last menstrual period for female subjects will be summarized as continuous variables using descriptive statistics.

Age group, gender, race, and ethnicity will be summarized as categorical variables using frequency counts and percentages.

History of tobacco and alcohol use will be summarized using frequency counts and percentages as:

- Alcohol use (Never, Current or Former).
- Tobacco use (Never, Current or Former).

All demographic and baseline characteristics will be presented in by subject listings.

7.4. Medical and Surgical History

Medical history will be coded using the MedDRA dictionary. The version to be used will be defined in the DMP. Medical and surgical history data will not be summarized; however, a subject listing for medical history will be provided for subjects in the Safety Population.

A separate listing for surgical history of the affected shoulder will also be provided.

7.5. Adhesive Capsulitis History

A listing for history of all past episodes of AC of the shoulder will be provided.

A separate listing for AC current symptomatology will also be provided.

7.6. **Prior/Concomitant Medications and Nondrug Therapies**

Prior and concomitant medication use will be summarized by treatment group and overall using frequency counts and percentages for subjects in the Safety Population, by active ingredient within each ATC, with ATC and active ingredients ordered alphabetically. Prior and concomitant non-drug therapies (procedures) will be summarized by treatment group and overall using frequency counts and percentages with name of the procedures ordered alphabetically. Multiple use of the same medication/nondrug therapy by a subject will be counted only once.

Listings of prior and concomitant medications and nondrug therapies will be provided for all subjects in the Safety Population. Similarly, a separate listing of prior medications and non-drug therapies for AC will also be provided.

7.7. Hand Dominance

Hand dominance will be summarized by treatment group and overall using frequency count and percentages for subjects in the Safety Population.

A listing for hand dominance will be provided.

7.8. Passive External Rotation

Passive external rotation at 0°, 45°, and 90° of abduction at screening will be summarized by treatment group and overall using absolute degrees, degrees and percent deficit of the affected shoulder compared to the contralateral shoulder for subjects in the Safety Population.

A listing for passive external rotation at 0°, 45°, and 90° of abduction will be provided.

7.9. Efficacy Analyses

Efficacy parameters will be summarized and analyzed by treatment group using the mITT Population.

For primary and secondary analysis, endpoints of the affected shoulder in the EN3835 treatment group will be compared to those in the placebo group.

7.9.1. Primary Analysis

7.9.1.1. Change from Baseline in Adapted ASES Composite Score

The primary endpoint is the change from baseline to the Day 95 Visit in the adapted ASES composite score.

MMRM will be performed to estimate change from baseline treatment effect at Day 64 and Day 95 Visits comparing active to placebo for the adapted ASES composite score in the affected shoulder. MMRM will be performed to estimate the least square (LS) means of change from baseline for EN3835 and placebo treatment. *P* values and 95% CIs for the treatment difference (EN3835 – Placebo) will be calculated by MMRM for the visits with treatment, visit, and an interaction of treatment and visit as fixed effected and repeated with visit/subject. Autoregressive covariance structure will be used in the model.

Observed values and change from baseline in the adapted ASES composite score in the affected shoulder for each treatment group will be summarized at Day 22, 43, 64 and 95 Visits using descriptive statistics.

A listing of adapted ASES scores will be provided.

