9.3.1. Efficacy Analysis

The primary endpoint is the change from baseline to the Day 95 Visit in the adapted ASES composite score.

A mixed-model ANOVA with factors for treatment group and visit will be performed to compare active to placebo for the change from baseline to the Day 95 Visit in adapted ASES composite score.

A mixed-model ANOVA with factors for treatment group and visit will be performed to compare active to placebo for the absolute and percent change from baseline to the Day 22, 43, 64, and Day 95 Visits in PROM, AROM, adapted ASES function subscale, and adapted ASES pain subscale.

For the Investigator Satisfaction with Treatment and Subject Satisfaction with Treatment at the Days 64 and Day 95 Visits, a Wilcoxon rank sum nonparametric test will be performed to compare active to placebo. A Wilcoxon rank sum nonparametric test will also be used to compare active to placebo for the change from baseline in Patient-reported Global Severity of Adhesive Capsulitis at the Day 22, 43, 64 and 95 Visits.

For Patient-reported Change in Severity of Adhesive Capsulitis at the Day 22, 43, 64, and 95 Visits, a chi-square test will be performed to compare active to placebo.

Endpoints of the affected shoulder in the EN3835 group will be compared to the endpoints of the affected shoulder in the placebo group.

The tertiary/exploratory analysis plan will be provided in the SAP.

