3.1.1. End-of-Study Definition

A subject is considered to have completed the study if the subject has completed the Day 95 Visit.

The end of the study visit is defined as the completion of the final assessment for the last subject enrolled in the trial.

A subject is considered evaluable if the subject is randomized, received at least 1 injection of study treatment, and has a valid baseline ASES composite score in the affected shoulder and at least 1 valid adapted ASES composite score after administration of study treatment. This includes both completers and early terminated subjects.

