4.7.1.3. Composite Score

The adapted ASES composite score is the sum of the pain subscale score (50% of the composite score) and the function subscale score (50% of the composite score). The calculation is:

Composite score = Pain subscale score + Function subscale score

25-April-2022

The range for the composite score is 0-100, where 0 is the worst pain and least functional and 100 is least pain and most functional. If either of the pain subscale or function subscale score is missing, then the ASES composite score will be considered as missing.

Change from baseline in the adapted ASES composite score for the affected shoulder at the Day 22, 43, 64, and 95 Visits will be analyzed. Positive change from baseline score means an improvement in pain and/or shoulder function from baseline.

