7.9.2.3. Change from Baseline in Adapted Pain and Function Subscale

MMRM will be performed to estimate change from baseline treatment effect at Day 22, 43, 64 and Day 95 Visits comparing active to placebo for adapted pain subscale and adapted function subscale in the affected shoulder. MMRM will be performed to estimate the LS means of change from baseline for EN3835 and placebo treatment. *P* values and 95% CIs for the treatment difference (EN3835 – Placebo) will be calculated by MMRM for the visits with treatment, visit, and an interaction of treatment and visit as fixed effected and repeated with visit/subject. Autoregressive covariance structure will be used in the model.

Observed values and change from baseline in adapted pain subscale and adapted function subscale in the affected shoulder for each treatment group will be summarized at Day 22, 43, 64, and 95 Visits using descriptive statistics.

In addition, score and change from baseline for each of the individual questions will be summarized for adapted function subscale for each treatment group using frequency counts and percentages with mean and SD.

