7.9.2.4. Change from Baseline in PUM Scale

MMRM will be performed to estimate change from baseline treatment effect at Day 64 and Day 95 Visit comparing active to placebo for PUM scale in the affected shoulder. MMRM will be performed to estimate the LS means of change from baseline for EN3835 and placebo treatment. *P* values and 95% CIs for the treatment difference (EN3835 – Placebo) will be

25-April-2022

calculated by MMRM for the visits with treatment, visit, and an interaction of treatment and visit as fixed effected and repeated with visit/subject. Autoregressive covariance structure will be used in the model.

Observed values and change from baseline in the PUM scale in the affected shoulder for each treatment group will be summarized at Day 64 and Day 95 Visits using descriptive statistics.

A listing of PUM scale scores will be provided.

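### The primary MMRM reads most naturally as a Day 64 and Day 95 model, which leaves Day 22 and Day 43 composite scores out of the primary test; name the four visits, the covariance and an early-termination rule

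*SAP*

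**What the plan says.** SAP 7.9.1.1 specifies the primary model as follows: "MMRM will be performed to estimate change from baseline treatment effect at Day 64 and Day 95 Visits comparing active to placebo". Its fixed effects are treatment, visit and their interaction. There is no baseline or early-score covariate. The same section adds "Autoregressive covariance structure will be used in the model". All four post-baseline visits appear only in the descriptive part, where observed values and changes "will be summarized at Day 22, 43, 64 and 95 Visits using descriptive statistics".

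Other passages bear on which visits enter the model:

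- SAP 4.7.1.3 says the change in "adapted ASES composite score for the affected shoulder at the Day 22, 43, 64, and 95 Visits will be analyzed".
- SAP 7.9.2.3, for the pain and function subscales that sum to the composite, says "MMRM will be performed to estimate change from baseline treatment effect at Day 22, 43, 64 and Day 95 Visits". SAP 7.9.2.1 and 7.9.2.2 name the same four visits for PROM and AROM.
- SAP 7.9.2.4 is the only other two-visit MMRM: "treatment effect at Day 64 and Day 95 Visit comparing active to placebo for PUM scale". The Schedule of Activities has no PUM assessment at Day 22 or 43.
- Protocol 9.3.1 specifies a mixed model "for the change from baseline to the Day 95 Visit in adapted ASES composite score" and does not list the visits fitted.

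On who counts, SAP 3.1.1 defines an evaluable subject by a valid baseline composite and one later composite at any visit: "This includes both completers and early terminated subjects". Table 15 says the same of the mITT Population, on which efficacy is analysed. Table 17 describes the primary analysis as missing at random.

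**The concern.** The visit lists differ between sections that otherwise share their wording, so the list appears to mark the visits modelled. If the primary model holds only Days 64 and 95, a subject whose post-baseline composites are all at Day 22 or 43 has no row in the likelihood, although that subject is in the mITT and is called evaluable. Missing at random then conditions on arm and, where it was observed, the Day 64 score. It cannot condition on early response.

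At stake is bias at Day 95 if subjects leave before Day 64 because of how they were responding and do so differently in the two arms. The one planned missing-data sensitivity analysis, the tipping-point analysis, is skipped when the primary p-value exceeds 0.05 (SAP 6.3.1 and 7.9.4.1). A bias toward zero would therefore go unexamined.

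**Working it through.** **Inputs from the documents** (Protocol 9.1, SAP 3.5): changes of 38.6 and 27.6, so a difference of 11.0; SD 21.6; two-sided 0.05; 85% power; 142 subjects; about 20% dropout; 180 dosed. The documents give no earlier SDs, correlations, dropout timing or dropout mechanism. Those are assumptions below.

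**The plan's own figure.** n per arm = 2 × (1.960 + 1.036)² × 21.6² / 11.0² = 69.2, so 70 per arm and 140 in all. The t-based calculation gives 85.4% power at 71 per arm, so 142 reproduces. Dropout: 142 / 0.8 = 177.5, rounded up to 178. With 180 dosed, leavers number 180 × 0.20 = 36, or 180 − 142 = 38 if exactly 142 complete.

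**Subjects with composites only at Day 22 or 43.** These are the leavers between the Day 22 and Day 64 visits, taking early-termination scores as unused.

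| Assumed timing of dropout | Fraction | Of 36 | Of 38 |
|---|---|---|---|
| From Day 22, even over three visit gaps | 2/3 | 24 | 25 |
| From Day 22, in proportion to days | 42/73 | 21 | 22 |
| From Day 1, even over four visit gaps | 2/4 | 18 | 19 |
| From Day 1, in proportion to days | 42/94 | 16 | 17 |

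The limits are 0 (all leave after Day 64) and 36–38 (all leave between Days 22 and 64). If dropout runs from Day 22 in proportion to days, every leaver attends an early-termination visit and its score goes to the nearest visit, the count is about 16: 36 or 38 × 31.5/73, with the Day 43/64 midpoint at Day 53.5.

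**Bias.** Let p be the fraction of an arm lost before Day 64, and g the shortfall of those subjects' true Day 95 mean below the whole-arm mean. A two-visit model recovers the Day 95 mean of those still present at Day 64, which is too high by p × g / (1 − p).

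Simulation: 1,000,000 subjects per arm; SD 21.6 at every visit; correlation 0.5 or 0.7 per visit step; 20% dropout per arm; logistic dropout on the current change score; dropout spread evenly after Days 22, 43 and 64, or all before Day 64; early-termination scores not used; true difference 11.0.

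| Dropout mechanism | Two-visit estimate |
|---|---|
| Random, or response-driven alike in both arms | about 11.0 |
| Poor improvers leave the active arm, odds ratio 1.65 per SD | 11.3–11.9 |
| Good improvers leave the active arm, odds ratio 1.65 per SD | 10.0–10.8 |
| Poor improvers leave the active arm, odds ratio 2.7 per SD | 11.5–12.7 |
| Good improvers leave the active arm, odds ratio 2.7 per SD | 9.3–10.5 |

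A four-visit unstructured model returned about 11.0 in every row. The formula agrees: in the most extreme case p = 0.20 and g is about 6.75, so the bias is 0.20 × 6.75 / 0.80 = 1.7, giving 12.7.

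**Precision under random dropout, constant SD (large-sample).** The Day 95 standard error is 3.53–3.57 on two visits and 3.44–3.56 on four, a reduction of 0.3% to 3.2%. Power is Φ(11.0/SE − 1.96): 86.9–87.6% on two visits and 87.1–89.2% on four.

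**Covariance.** True type I error at nominal 5% for equal-variance AR(1) is 4.3–5.9% on two visits. On four visits it is 4.8–5.1% if the SD is constant, 6.7–10.8% if it rises (assumed profiles from 18/20/21/21.6 to 13/17/20/21.6) and 2.7–4.4% if it falls (from 23/22.5/22/21.6 to 26/24.5/23/21.6). Heterogeneous AR(1) on four visits gives 4.3–5.0%.

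**The case against.** The strongest reply is that the two-visit model is inferred. The sentence can be read as naming the contrasts to report, and SAP 4.7.1.3 promises analysis at all four visits. That stands as a reason for caution. It does not reverse the reading, given the four-visit wording for the subscales and the match with PUM.

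A reader might infer that scores collected from early leavers are certainly discarded. The documents do not establish this. Early termination shares the Day 95 column of the Schedule of Activities, and the interim analysis counts the two together. If early-termination scores were analysed as Day 95, leavers who attend would enter even a two-visit model. SAP 6.3.1 lists discontinuation before Day 95 as a reason for a missing value, but that also fits leavers who skip the visit or withdraw consent.

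A reader might infer that the primary estimate is biased. Nothing in the documents shows response-driven dropout that differs by arm, and without that difference the bias is about nil.

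A reader might infer that enlarging the trial for early termination contradicts the model. It does not: the increase to 180 was sized so that 142 complete, and power never relied on leavers' early scores.

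A reader might attach the 6.7–10.8% error rates to the primary test. They describe an equal-variance AR(1) over four visits with an assumed rising SD, which the two-visit reading does not specify.

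Finally, the tipping-point imputation starts from a zero shift and may use Days 22 and 43, since its visit list is a placeholder. If so, a false-positive bias would be partly checked. Bias toward zero would not.

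**Conclusion.** The concern holds as an under-specified primary model with a cheap improvement available, not as a demonstrated error in the primary test. The two-visit reading is the better supported one. On it, and with no early-termination score assigned to Day 64 or 95, about 16 to 25 of 180 subjects would add nothing to the primary comparison. Missing at random would condition only on arm and Day 64.

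The effect on the estimate ranges from none to about 0.3–1.0 points under moderate one-arm response-driven dropout, and to 1.7 points at the extreme, against a planned difference of 11.0. These sizes rest on assumed correlations, timing and mechanism. The case for change is protection against bias and a reproducible specification. The precision gain is small, and planned power is met either way under the plan's own difference and SD.

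**What to change.** Issue a dated SAP revision before unblinding, written by blinded staff, that does the following:

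1. Enters Days 22, 43, 64 and 95 in the primary MMRM, with Day 95 as the sole primary contrast.
2. Changes the covariance at the same time to unstructured, with a stated fallback such as heterogeneous AR(1). Adding visits while keeping an equal-variance AR(1) could misstate the Day 95 error if the SD changes over time.
3. Assigns each early-termination score to the nearest analysis visit by study day, not automatically to Day 95.
4. If two visits are intended, says so and gives the reason, and still states the early-termination rule.

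No new data are needed. The cost is ten covariance parameters instead of two on about 180 subjects, and a changed primary model to record in Table 17. Day 22 and Day 43 composite contrasts come from the same fit as a by-product; their absence is not a separate defect.

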9. STATISTICAL CONSIDERATIONS AND METHODS

9.1. Sample Size Determination

A post hoc analysis was conducted using a subgroup of AUX-CC-871 subjects who were rated with moderate/severe AC based on baseline MRI images. This subgroup displayed a notable treatment effect (EN3835 vs placebo) on the pain and composite components of the adapted ASES questionnaire. This subgroup also displayed a treatment effect trend for the functional component of the adapted ASES. Given this result, the sample size calculation is based on the mean and SD found in this subgroup for the adapted ASES composite score on Day 95. Given a mean change from baseline value of 38.6 for the EN3835 group and 27.6 for the placebo group with an SD of 21.6, a sample size of approximately 142 subjects would be required given a 1:1 randomization and a type I error of 0.05 with a power of 85%. With an expected drop-out rate of approximately 20%, 180 subjects (90 EN3835 and 90 placebo) should be dosed to ensure 142 subjects complete the study.

9.2. **Populations for Analysis**

For the purposes of analysis, the following populations are defined:

- The Safety Population is defined as all randomized subjects who received at least 1 injection of study treatment (EN3835 or placebo). All safety analyses will be based on this population.
- The Intent-to-Treat (ITT) Population is defined as all randomized subjects who received at least 1 injection of study treatment (EN3835 or placebo).
- The Modified Intent-to-Treat (mITT) Population is defined as all ITT subjects who have a valid baseline adapted ASES composite score in the affected shoulder and at least 1 valid adapted ASES composite score after the injection of the study treatment. All efficacy analyses will be based on this population.
- The Per-Protocol (PP) Population is defined as those subjects in the mITT Population who do not have any major protocol deviations. Determination of PP subjects will be completed before the study database is closed and locked. If more than 10% of the mITT Population is excluded from the PP Population, then all efficacy summaries will be repeated using the PP Population for the sensitivity analysis.

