4.7.2. Passive Range of Motion (PROM) and Active Range of Motion (AROM)

The PROM and AROM in affected shoulder at Day 22, 43, 64 and 95 will be analyzed for the following motions:

- Forward flexion.
- Internal Rotation.
- External rotation.
- Abduction.
- Shoulder extension.

The PROM and AROM will be analyzed at Day 22, 43, 64 and 95 using the following endpoints:

- Absolute change from baseline in affected shoulder
- Absolute and percent change from baseline in affected shoulder compared to the contralateral shoulder. The calculation is as below:

Let

ASi: Measurement from affected shoulder at visit i

CS1: Measurement from contralateral unaffected shoulder at baseline

then

Di = ASi - CS1

D1 (Baseline value) = AS1 - CS1

Absolute change = Di - D1

Percent change from baseline at Visit i = ((Di - D1) / D1) * 100

In addition, the HBB values will be ordinal ranked based on the level a subject can reach behind the back. The higher ranked assessment value signifies the ability to reach higher up behind the back. The lower the ranked value signifies the ability to reach behind the back low. A value of 0 will be assigned to subjects that cannot reach behind the back at all (the lowest rank possible).

The observed and change from baseline in HBB values will be analyzed at the Day 22, 43, 64 and 95 Visits.

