5. ANALYSIS POPULATIONS

The study will use the following analysis populations for data summaries.

Population	Definition	Displays	
Safety Population	The Safety Population is defined as all randomized subjects who received at least 1 injection of study treatment (EN3835 or placebo).	All demographic, baseline characteristics and safety parameters will be summarized based on this population.	
	Subjects will be included in the Safety Population based on the actual treatment received.		
Intent-to-Treat (ITT) Population	The ITT Population is defined as all randomized subjects who received at least 1 injection of study treatment (EN3835 or placebo). Subjects will be included in the ITT Population based on the planned treatment.		
Modified Intent-to-Treat (mITT) Population	The mITT Population is defined as all ITT subjects who have a valid baseline adapted ASES composite score in the affected shoulder and at least 1 valid adapted ASES composite score after administration of study treatment.	All efficacy analyses will be based on this population.	
	Subjects will be included in the mITT Population based on the planned treatment. Any subjects in the mITT Population are considered evaluable subjects, including early terminated subjects and/or completers.		
Per-Protocol (PP) Population The PP Population is defined as those subjects in the mITT Population who do not have any major protocol deviations which have a significant effect on the primary endpoint.		If more than 10% of the mITT Population is excluded from the PP Population, then select efficacy summaries will be repeated using the PP Population for the sensitivity analysis.	

Table 15:Analysis Populations

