6.2. Derived Variables

Table 16 defines the derived variables for study parameters.

Variable	Definition	
Height (cm)	If height is recorded in inches, then height is equal to the recorded value multiplied by 2.54 and then rounded to 1 decimal place.	
Weight (kg)	If weight is recorded in pounds, then weight is equal to the recorded value multiplied by 0.454 and then rounded to 1 decimal place.	
Body Mass Index (BMI)	BMI will be computed using height and body weight measured at Screening as, BMI $(kg/m^2) =$ Weight $(kg) /$ Height $(m)^2$	
Relative Day 1	The day of first injection of study drug will be considered as relative Day 1.	
Study Day (for assessment on or after Day 1)	Study Day will be computed as, Date of Assessment – Date of Day 1 + 1	
Study Day (for assessment before Day 1)	Study Day will be computed as, Date of Assessment – Date of Day 1	
Baseline	Baseline is defined as the last non-missing measurement/assessment prior to the first dose of study drug.	
	The assessments made in unscheduled visits will be considered in calculation of baseline, if the unscheduled assessment is the closest value preceding the first dose of study drug.	
Baseline for Vital Signs on Injection Days	For vital signs on injection days, the baseline value will be the vital sign measure immediately prior to the first dose of study drug.	
Change from Baseline	Change from baseline will be derived as, post-baseline visit/time point value – the baseline value.	
Last Date in Study	Last date in study is defined as:	
	• The date of End of Study (EOS) Visit (Day 95) if the subject completes the study	
	• The date of early termination visit if the subject is terminated early from study at a non-scheduled visit	
	• The date of the latest scheduled visit if the subject is terminated early from study at a scheduled visit or lost to follow-up.	
Duration of AE	AE end date – AE start date + 1	
AE Onset Day (for AE onset date on or after date Day 1)	AE start date – Date of Day 1 + 1	
AE Onset Day (for AE onset date before date of Day 1)	AE start date – Date of Day 1	

Table 16:Derived Variables and Definition

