 - All arms with identical adjustment: $\delta_P = \delta_A$ and $\delta_A = 0$ to Δ_1
- The imputation will be performed using SAS PROC MI with the MONOTONE statement and the REGRESSION option with the following specifications:

```
PROC MI DATA=IN_MCMC NIMPUTE=1 (see note) SEED=234 OUT=OUTPUT;
VAR ...; (treatment group, baseline covariates, and the preceding non-missing values in
the order of clinical visits: baseline, Visit X, ..., Visit Y)
CLASS...; (treatment group)
MONOTONE REG (/details);
MNAR ADJUST (Visit X / SHIFT=delta_a ADJUSTOBS=(TRT01PN ='1'));
MNAR ADJUST (Visit Y / SHIFT=delta_a ADJUSTOBS=(TRT01PN ='1'));
MNAR ADJUST (Visit Y / SHIFT=delta_a ADJUSTOBS=(TRT01PN ='1'));
MNAR ADJUST (Visit X / SHIFT=delta_a ADJUSTOBS=(TRT01PN ='1'));
MNAR ADJUST (Visit X / SHIFT=delta_p ADJUSTOBS=(TRT01PN ='0'));
MNAR ADJUST (Visit Y / SHIFT=delta_p ADJUSTOBS=(TRT01PN ='0'));
MNAR ADJUST (... / SHIFT=delta_p ADJUSTOBS=(TRT01PN ='0'));
```

Note: NIMPUTE=n if MCMC was NOT applied at the previous step.

Step 3: Analysis and Pooling

For each value of δ_P and δ_A , MMRM described in section 7.9.1 will be performed for each of the n adjusted fully imputed datasets. The analysis results obtained will be combined into a single estimation using PROC MIANALYZE to produce final inferences.

The following estimates will be presented in the sensitivity analysis table:

- 1. LSM estimate for the mean change from baseline at the visit where primary endpoint is measured for each treatment.
- 2. LSM estimate for treatment difference of the mean change from baseline at the visit where primary endpoint is measured and the corresponding 2-sided 95% CI and p-value for change from baseline in the primary endpoint will be provided.

Shift parameters will begin with active-only adjustment, followed by a control adjustment that is half of the active adjustment, followed by all arms with identical shift adjustments, as stated in Step 2.

25-April-2022

All steps above are repeated with different values of the shift parameter until the tipping point is reached or all possible values are explored. The tipping point can be identified when the result is no longer statistically significant (p-value >0.05). It is possible a tipping point is not reached if little to no data is missing.

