8. CHANGE FROM PROTOCOL

This SAP is prepared based on the study protocol; original version dated April 06, 2020, Amendment 1 dated July 10, 2020, Amendment 2 dated July 31, 2020, Amendment 3 on November 06, 2020, and Amendment 4 on October 22, 2021.

Table 17 lists any significant changes in the SAP from what is proposed in the protocol.

Text in Protocol	Change in SAP	Justification
The Per-Protocol (PP) Population is defined as those subjects in the mITT Population who do not have any major protocol deviations.	The PP Population is defined as those subjects in the mITT Population who do not have any major protocol deviations which have a significant effect on the primary endpoint.	Change the PP Population to emphasize only subjects with major PDs that effect the primary endpoint to be excluded. This allows subjects with major PDs related to safety only (and no effect on primary endpoint) to be included in PP Population.
N/A	Added a tipping point sensitivity analysis (section 7.9.4)	Tipping point analysis checks if the missing data effects the primary analysis conclusions by checking severity of missing data. Identify the tipping poing where treatment effect in subjects with missing data overturns the significant treatment effect otbtained in the missing at random primary analysis.

Table 17:Changes from Protocol

9. **REVISION HISTORY**

Non-editorial changes made to any of the modules of this SAP will be recorded in Table 18.

Table 18:Revision History

Version	Date	Revision Author	Comments
v1.0	Aug 12, 2020		Original version
v2.0	April 25, 2022		Protocol amendment updates, prior/concomitant definition, adverse events of special interest, tipping point sensitivity analysis

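### The primary MMRM of change in adapted ASES composite omits the baseline score, forgoing a nearly free gain in precision of unknown size (none to about 8 power points)

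*SAP*

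**What the plan says.** The primary endpoint is the change from baseline to Day 95 in the adapted ASES composite. SAP 7.9.1.1 fits an MMRM with an autoregressive covariance "with treatment, visit, and an interaction of treatment and visit as fixed effected and repeated with visit/subject". No covariate is listed. Protocol 9.3.1 is equally bare: "A mixed-model ANOVA with factors for treatment group and visit will be performed to compare active to placebo".

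The outcome already uses baseline by subtraction. In SAP 6.2, Table 16, "Change from baseline will be derived as, post-baseline visit/time point value" has the baseline value taken off it.

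The covariate exists for everyone analysed. SAP section 5 limits the mITT Population to "all ITT subjects who have a valid baseline adapted ASES composite score in the affected shoulder" who also have at least one valid post-treatment composite.

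Baseline covariates are mentioned in only one model, the imputation step of the tipping-point analysis (SAP 7.9.4.1). That analysis runs only if the primary result is significant. In Step 3, the "MMRM described in section 7.9.1 will be performed for each of the" imputed datasets, so baseline drops out again at the analysis stage. SAP section 8 says that "Table 17 lists any significant changes in the SAP from what is proposed in the protocol", and no covariate is among them.

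The MMRMs for the pain and function subscales, PUM and range of motion (SAP 7.9.2.1 to 7.9.2.4) have the same form.

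**The concern.** Subtracting baseline is not the same as adjusting for it. A change score assumes that each extra baseline point carries through as exactly one extra point at Day 95. Where that slope is not 1, change remains correlated with baseline. That correlation stays in the error term, and a chance baseline difference between arms is over- or under-corrected.

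A slope below 1 is plausible. The composite is capped at 100, so a subject can improve by at most 100 minus the baseline score, and the planning mean changes are large (27.6 and 38.6). The documents do not say how far the slope is from 1.

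What is at stake is precision in the primary comparison. Type I error, bias over randomizations and the sample-size figure are not in question.

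**Working it through.** **Inputs from the documents** (Protocol 9.1, SAP 3.5, SAP 6.1): mean changes 38.6 and 27.6, so the difference is 11.0; SD of change 21.6; two-sided alpha 0.05; 142 evaluable, 71 per arm.

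**Inputs that must be assumed:** the correlation r between baseline and change, or equivalently the baseline SD and the baseline-to-Day 95 correlation. Neither document gives them.

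**Step 1, the plan's own figure.** The standard error is 21.6 × √(2/71) = 3.63. A two-sample t test with 140 df has 85.4% power, and 71 is the smallest number per arm that reaches 85%. The stated 142 is reproduced.

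**Step 2, power after adjustment.** Residual SD = 21.6 × √(1 − r²), non-central t with 139 df. The third column also multiplies the variance by 1 + 1/(142 − 4) for estimating the slope.

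| Absolute r | Residual SD | Power | Power with slope penalty |
|---|---|---|---|
| 0 | 21.6 | 85.4% | 85.1% |
| 0.1 | 21.5 | 85.7% | 85.5% |
| 0.2 | 21.2 | 86.8% | 86.5% |
| 0.3 | 20.6 | 88.5% | 88.2% |
| 0.4 | 19.8 | 90.8% | 90.6% |
| 0.5 | 18.7 | 93.6% | 93.4% |

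The 95% CI half-width falls from 7.2 points at r = 0 to 6.2 at 0.5. The worst case is a loss of 85.4 − 85.1 = 0.3 points. At 0.5 the gain is 93.6 − 85.4 = 8.2 points, or 8.0 with the penalty.

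**Step 3, what r means in terms of the scores.** Hold the SD of change at 21.6. For baseline SD sb and baseline-to-Day 95 correlation ρ, solve sy² + sb² − 2ρ·sy·sb = 21.6² for the Day 95 SD sy. Then slope = ρ·sy/sb and r = (ρ·sy − sb)/21.6.

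- The gain is zero at ρ = sb/√(21.6² + sb²), which is 0.42, 0.49 and 0.57 for sb = 10, 12 and 15.
- sb = 12, ρ = 0.3: sy = 21.9, slope 0.55, r = −0.25, power 87.6%.
- sb = 12, ρ = 0.5: sy = 24.9, slope 1.04, r = 0.02, power 85.4%.

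**Step 4, chance imbalance.** With sb = 12, a one-standard-error baseline difference is 12 × √(2/71) = 2.0 points. At slope 0.55 the change score over-corrects by 0.45 × 2.0 = 0.9 points. At slope 1.04 the error is 0.04 × 2.0 = 0.1 points.

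These are single-visit, complete-data approximations to the Day 95 contrast, not simulations of the autoregressive MMRM.

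**The case against.** The strongest reply is that this is optional efficiency. The planned test is valid, protocol and SAP agree with each other, and the study has its stated power without adjustment. All of that is right.

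The upper end of the range is also an assumption. For an absolute r of 0.5, ρ must be −0.04 or 0.74 at a baseline SD of 10, 0.06 or 0.77 at 12, and 0.22 or 0.81 at 15. For ρ between 0.3 and 0.6, power is at most 87.7% at SD 10 and 87.6% at SD 12, a gain of 0 to 2.3 points. At SD 15 it reaches 91.0% at ρ = 0.3. Entry requires a function subscale below 35 of 50, which narrows the baseline spread and favours the lower part of the range. This stands: a gain of a few points or less is quite possible, and 0.5 is neither a forecast nor a ceiling.

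The slope penalty applies at every r, not only at zero. It takes 0.2 to 0.3 points off each figure and does not alter the picture.

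Timing is a fair caution. SAP v2.0 is dated 25 April 2022 and the last subject was expected to complete in June 2022. The documents do not say whether the interim had been held, and its futility rule is in a separate document that may rely on the primary model.

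Finally, no gain has been worked out for the secondary models, so the case there is consistency of form. None of these points makes adjustment harmful.

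**Conclusion.** The concern holds. The primary model leaves out a prognostic candidate that is recorded for every analysed subject. Under absolute baseline-change correlations of 0 to 0.5, the forgone power lies between none and about 8 points, and the most that adjustment could cost is about 0.3. Where in that range the trial falls cannot be told from the documents. The figures rest on 71 per arm, a difference of 11.0 and an SD of change of 21.6.

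There is a second, unquantified benefit. Amendment 4 raised enrolment because early termination was higher than expected. An MMRM's missing-at-random assumption conditions only on what is in the model, so including baseline would also cover dropout related to the baseline score. It would also bring the analysis model into line with the tipping-point imputation model, which already conditions on baseline covariates.

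This is worth doing, but it is a gain in precision and not the repair of an invalid analysis.

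**What to change.** Before database lock and unblinding:

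- In SAP 7.9.1.1, add baseline adapted ASES composite and baseline-by-visit as fixed effects. Carry the same terms into the Step 3 refit in 7.9.4.1.
- In the subscale, PUM and absolute-change range-of-motion MMRMs (7.9.2.1 to 7.9.2.4), add the affected-shoulder baseline of the same measure. For the change referenced to the contralateral shoulder, use the baseline in SAP 4.7.2, "D1 (Baseline value) = AS1 - CS1".
- The percent-change range-of-motion models, whose outcome already divides by D1, can stay as they are. This limits the scope of the edit; dividing by baseline is not itself an adjustment for it.
- Add a row to Table 17. Check whether the separate interim document and the table shells refer to the primary model, and align them if they do.

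**Cost:** text edits and programming only, with no new data or subjects. The primary model gains 2 parameters if only Day 64 and Day 95 are fitted, or 4 if all four post-baseline visits are. The sample size stands, because it uses the unadjusted SD of change.
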